**Table 9: Multiplication Factor for each Severity Score for Each Phenomenology (Study RVT-101-2001)**

	1.1 CVH	1.2 Illusion	1.3 Presence	1.4 Passage	1.6 SVH
Multiplication factor	4	3	1	1	1

The Total Severity Score is the sum of the 5 phenomenology Adjusted Total Severity scores (and thus the Total Severity Score ranges from 0 to 90, with higher scores indicating worse overall severity of hallucination phenomena).

**5.7.2. Section 3 Scoring (Distress Caused by the Hallucinations)**

Section 3 applies to the phenomenology having the highest impact on the patient, where impact is determined in response to Question 2.3 in Table 8). If there is only one phenomenology present and the response to Question 2.3 is missing, the one phenomenology that is present will be used for the distress scoring. There are 6 questions relating to the distress, broken up into 3 areas:

- Emotions
  - Do you find the content of your hallucinations irritating?
  - Do you find the content of your hallucinations distressing?
- Cognitions
  - Does the content of your hallucinations make you worry that you are losing your mind?
  - While you are having a hallucination do you ever believe it is real?
- Behaviors
  - Do you ever act out on the content of your hallucinations?
  - Are you able to ignore your hallucinations, i.e. make them stop?

The Distress Score is the sum of all 6 questions. The minimal distress score is 0 and the highest (worst) distress score is 18.

Missing responses for the Distress Score will be handled as follows:

- If only 1 response is missing, the value for the response will be imputed as the average of the remaining 5 non-missing questions.
- If >1 response is missing, the Distress Score will be set to missing.

### 5.7.3. Analysis of NEVHI Outcomes

Data will be presented in two ways:

1. Number (%) of patients:
  - a. worsening from baseline
  - b. remaining unchanged from baseline
  - c. improving from baseline.

This would be performed for each score separately (Total Severity Score and Distress Score). Patients with NO hallucinations (a Phenomenology score of 0) at a given visit would have a score of 0 for Severity and for Distress at that visit.

2. Mean changes over time in the Section 1 Total Score, the Total Severity Score and Distress Score.

### 5.8. Clinician Assessment of Fluctuation (CAF)

The CAF assesses fluctuating cognition and impaired consciousness over the previous month (Walker 2000). The CAF is one of the measures of cognitive fluctuation recommended by the DLB Consortium when applying the DLB diagnostic criteria (McKeith 2005).

The CAF is a 2-item questionnaire that asks about fluctuating cognition and fluctuation confusion, with each question reported as Yes, No, and Not Known.

- **Fluctuating Cognition:** Does the patient ever have spontaneous impaired alertness and concentration, ie, appear drowsy but awake, look dazed, not be aware of what is going on around? (Clear examples demonstrating impaired consciousness with variations in performance/cognition are required to receive a positive rating.) Have these episodes occurred within the last month?
- **Fluctuation Confusion:** Has the level of confusion experienced by the patient tended to vary a lot recently from day to day or week to week? Has it become worse, then improved for a while, ie, been up and down? (Significant fluctuation is regarded as present if distinct examples of differences in performance/cognition can be given on at least two occasions over the past month.)

If fluctuation is reported as ‘yes’, frequency (Table 10) and duration (Table 11) scores are assessed. These scores (frequency and duration) are multiplied to achieve a severity score (Van Dyk 2015).

- If the clinician assessment of fluctuation is that the patient does not have fluctuation, the patient is assigned a severity score of 0 for that question.

**Table 10: Frequency of Fluctuating Cognition or Confusion Scores (Study RVT-101-2001)**

Frequency of fluctuating Cognition or Confusion	
1	1 per month
2	Monthly – Weekly

3	Weekly – Daily
4	≥ Daily

**Table 11: Duration of Fluctuating Cognition or Confusion Scores (Study RVT-101-2001)**

Duration of fluctuating Cognition or Confusion	
0	seconds
1	< 5 minutes
2	5 minutes – 1 hour
3	> 1 hour
4	> 1 Day

If either frequency or duration is missing for either question, the severity score is set to missing.

These data will be analyzed as follows for each question separately, by visit:

- The number (%) of patients with cognition (or confusion) will be tabulated..
- For each question, changes over time in severity scores.
- The number (%) of patients with EITHER a ‘yes’ on cognition OR a ‘yes’ on confusion (or a YES on both) vs those with a ‘no’ on BOTH.

### 5.9. Dependence Scale (DS)

The DS measures the amount of assistance patients with dementia require in performing daily activities [Brickman 2002]. The caregiver answers questions about the dependency of the subject. The scale consists of 13 items. A total score will be calculated via summing the scores, with a range from 0 to 15 with higher scores indicating greater dependency.

No imputation for missing values is performed; thus, if an item is missing, the corresponding domain is not calculated (ie, is set to missing).

### 5.10. EuroQol-5D (EQ-5D)

The EQ-5D is a standardized measure of health status that provides a measure of health-related quality of life that is widely used in clinical trials [Rabin 2001]. For this study the EQ-5D will be a caregiver proxy assessment. The assessment will be completed by the caregiver and will assess the caregiver’s impressions of how the subject would rate his/her own quality of life.

The EQ-5D questionnaire consists of 2 components: the EQ-5D descriptive system and the EQ visual analogue scale (EQ-VAS). The EQ-VAS records overall health status on a 20 cm vertical line with a score of 0 (worst health one can imagine) to 100 (best health one can imagine).

The EQ-5D comprises the following five dimensions:

- Mobility
- self-care
- usual activities
- pain/discomfort

- anxiety/depression

Each dimension has 5 response levels:

- no problem
- slight problems
- moderate problems
- severe problems
- extreme problems

The number and percentage by response level will be summarized by visit and treatment for each domain. The response levels will be dichotomized to show number and percentage of subjects without problems (reported no problems) and with problems (slight problems, moderate problems, severe problems, and extreme problems).

### **5.11. Modified Circadian Sleep Inventory – (CSI)**

The Circadian Sleep Inventory is a two-part questionnaire that assesses sleep-related problems and behaviors. In this study, modifications have been made to remove questions assessing sleep apnea and restless leg syndrome.

The CSI has a Likert scale (How would you rate the overall quality of your subject's sleep in previous 4 weeks?).

The modified CSI also contains 12 questions that are answered by the caregiver about the subject's sleep-related behaviors, and an overall sleep quality rating. For each question, both the frequency and the severity of each behavior are determined and are multiplied. The CSI total score will be calculated as the sum of the scores for all questions. Note that if an answer to an item is 'no', the item score is zero. If the answer to an item is 'Don't know', the item score is set to missing.

A single missing value is allowed, with the mean of the 11 non-missing items used as the imputed value for that missing value.

### **5.12. Mini-Mental State Evaluation (MMSE)**

While the MMSE is not specifically an endpoint, it is used to measure baseline disease severity, and therefore is included in the descriptions in this section.

The MMSE [Folstein 1975] consists of 11 tests of orientation, memory (recent and immediate), concentration, language and praxis. Scores range from 0 to 30, with lower scores indicating greater cognitive impairment. The MMSE score is the sum of the 11 items; if any item is missing then the total score will be set to missing.

### **5.13. Cognitive Drug Research (CDR) Computerized Assessment System**

The CDR computerized assessment system is a computerized battery of cognitive tests (Simpson 1991; Keith 1998). The CDR computerized assessment includes tests of attention and information processing speed (Simple Reaction Time, Choice Reaction Time, and Digit

Vigilance), verbal and visuospatial working memory (Numeric and Spatial Working Memory) and verbal and visual episodic memory (Immediate and Delayed Word Recall, Word Recognition and Picture Recognition).

The CDR computerized assessment will be administered at the study sites by trained administrators. During the Screening visit (Visit 1) and Visit 2, the CDR computerized assessment will be administered as training sessions to overcome test anxiety, ensure the patient is able and willing to undergo testing, and overcome initial training effects in order that a stable score is subsequently obtained at Baseline (Visit 3). All tasks are computer-controlled. The information is presented on the screen of a notebook computer and the responses recorded via a response module containing two buttons, one marked 'NO' and the other 'YES'. The test administrator sits with the patient throughout testing, explains each test using pre-set instructions, initiates each test and ensures the patient performs it appropriately.

When possible, the CDR computerized assessment should always be the first assessment conducted, and should be administered, within  $\pm 1$  hour of the time of Baseline administration at all subsequent visits to control for potential impact of circadian variation in performance.

The tests are administered in the following order:

- Immediate Word Recall: A list of 12 words is presented on the screen at the rate of 1 every 2 seconds for the patient to remember. The patient is then given 1 minute to recall as many of the words as possible.
- Picture Presentation: A series of 14 pictures is presented on the screen at the rate of 1 every 3 seconds for the patient to remember.
- Simple Reaction Time: The patient is instructed to press the 'YES' response button as quickly as possible every time the word 'YES' is presented on the screen. Thirty stimuli are presented with a varying inter-stimulus interval.
- Digit Vigilance: A target digit is randomly selected and constantly displayed to the right of the screen. A series of digits is then presented in the center of the screen at the rate of 80 per minute and the patient is required to press the 'YES' button as quickly as possible every time the digit in the series matches the target digit. There are 15 targets in the series. The task lasts for 3 minutes.
- Choice Reaction Time: Either the word 'NO' or the word 'YES' is presented on the screen and the patient is instructed to press the corresponding button as quickly as possible. There are 30 trials for which each stimulus word is chosen randomly with equal probability and there is a varying inter-stimulus interval.
- Spatial Working Memory: A picture of a house is presented on the screen with 4 of its 9 windows lit. The patient has to memorize the position of the lit windows. For each of the 36 subsequent presentations of the house, the patient is required to decide whether or not the 1 window that was lit was also lit in the original presentation. The patient responds by pressing the 'YES' or 'NO' buttons as appropriate, as quickly as possible.
- Numeric Working Memory: A series of 3 digits is presented for the patient to hold in memory. This is followed by a series of 18 probe digits for each of which the patient

has to decide whether or not it is in the original series and press the 'YES' or 'NO' response button as appropriate, as quickly as possible.

- Delayed Word Recall: The patient is again given 1 minute to recall as many of the words as possible.
- Word Recognition: The original words plus 12 distracter words are presented one at a time in a randomized order. For each word the patient is required to indicate whether or not the patient recognizes it as being from the original list of words by pressing the 'YES' or 'NO' button as appropriate, as quickly as possible.
- Picture Recognition: The original pictures plus 14 distracter pictures are presented one at a time in a randomized order. For each picture the patient has to indicate whether or not the patient recognizes it as being from the original series by pressing the 'YES' or 'NO' button as appropriate, as quickly as possible.

Seven domains will be calculated from the CDR computerized assessment system tests (Power of Attention, Continuity of Attention, Cognitive Reaction Time, Response Variability, Quality of Working Memory, Quality of Episodic Secondary Memory, and Speed of Memory). [Table 12](#) and [Table 13](#) provide details on how these 7 domains are calculated.

**Table 12: CDR Computerized Assessments System Variables (Study RVT-101-2001)**

Task Name	Variable	Abbreviation	Unit
Immediate Word Recall	Words Recalled Correctly	IRCL	#
	Errors	IRCLERR	#
Simple Reaction Time	Mean Reaction Time	SRT	ms
	Median Reaction Time	SRTM	ms
	Standard Deviation	SRTSD	ms
Digit Vigilance	Mean Reaction Time	VIGRT	ms
	Accuracy	VIGACC	%
	False Alarms	VIGFA	#
	Standard Deviation	VIGSD	ms
Choice Reaction Time	Mean Reaction Time	CRT	ms
	Median Reaction Time	CRTM	ms
	Accuracy	CRTACC	%
	Standard Deviation	CRTSD	ms
Spatial Working Memory	Median Reaction Time	SPMRTM	ms
	Sensitivity Index	SPMSI	SI
Numeric Working Memory	Median Reaction Time	NWMRTM	ms
	Sensitivity Index	NWMSI	SI
Delayed Word Recall	Words Recalled Correctly	DRCL	#
	Errors	DRCLERR	#
Word Recognition	Median Reaction Time	DRECRTM	ms
	Original Stimuli Accuracy	DRECOACC	%
	New Stimuli Accuracy	DRECNACC	%
Picture Recognition	Median Reaction Time	DPICRTM	ms
	Original Stimuli Accuracy	DPICOACC	SI
	New Stimuli Accuracy	DPICNACC	

**Table 13: Calculation of CDR Computerized Assessment System Domain Scores (Study RVT-101-2001)**

Name	Abbreviation	Unit	Calculation	Interpretation
Power of Attention	POW-ATT	ms	SRTM+VIGRT+CRTM	Lower scores are better
Continuity of Attention	CONT-ATT	#	(VIGACC*0.45)+(CRTACC*0.5)-VIGFA	Higher scores are better
Cognitive Reaction Time	COGRT	ms	CRTM-SRTM	Lower scores are better
Response Variability	POWATTCV	%	(SRTSD/SRT*100)+(CRTSD/CRT*100)+(VIGSD/VIGRT*100)	Lower scores are better
Quality of Working Memory	QL-WORK	SI	SPMSI+NWMSI	Higher scores are better
Quality of Episodic Secondary Memory	QL-EPIS	#	(DRECOACC+DRECNACC-100)+(DPICOACC+DPICNACC-100)+((IRCL-IRCLERR)*100/12)+ ((DRCL-DRCLERR)*100/12)	Higher scores are better
Speed of Memory	SPEEDMEM	ms	SPMRTM+NWMRTM+DRECRTM+DPICRTM	Lower scores are better

Based on the derived domain scores, a standardized z-score will be derived for each CDR system domain using the formula below:

$$\text{Domain z-score} = (X2 - X1)/SD1$$

Where:

X2 is the domain score for each individual at any study assessment time post Baseline

X1 is the Baseline domain score for that individual

SD1 is the domain standard deviation of the population at Baseline

A composite z-score for the 7 CDR domains will be calculated based on the individual domain scores as:

$$(\text{Continuity of Attention z-score} + \text{Quality of Episodic Secondary Memory z-score} - \text{Response Variability z-score} + \text{Quality of Working Memory z-score} - \text{Power of Attention z-score} - \text{Cognitive Reaction Time} - \text{Speed of Memory z-score})/7$$

Missing data will be handled as follows:

- If any individual item (variable) is missing for a Domain Score, the Domain Score will be set to missing. Thus, no imputation of individual Domain Scores will be performed; all variables are needed in order to calculate each Domain Score.
- If a single Domain Score is missing for the derivation of the Composite score (ie, one of the 7 Domain Scores is missing), the average of the 6 non-missing Domain z-scores will be used to replace the missing Domain z-score.
- If >1 Domain Scores are missing, the Composite score will be set to missing.

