**Table 4 Calculation of CDR Computerized Assessment System Domain Scores**

Name	Abbreviation	Unit	Calculation
Power of Attention	POW_ATT	ms	SRTM+VIGRT+CRTM
Continuity of Attention	CONT_ATT	#	(VIGACC*0.45)+(CRTACC*0.5)-VIGFA
Cognitive Reaction Time	COGRT	ms	CRTM-SRTM
Response Variability	POWATTCV	%	(SRTSD/SRT*100)+(CRTSD/CRT*100)+(VIGSD/VIGRT*100)
Quality of Working Memory	QL_WORK	SI	SPMSI+NWMSI
Quality of Episodic Secondary Memory	QL_EPIS	#	(DRECOACC+DRECNACC-100)+(DPICOACC+DPICNACC-100)+((IRCL-IRCLERR)*100/12)+((DRCL-DRCLERR)*100/12)
Speed of Memory	SPEEDMEM	ms	SPMRTM+NWMRTM+DRECRMTM+DPICRTM

Based on the derived domain scores, a standardized z-score will be derived for each CDR system domain using the formula below:

$$\text{Domain z-score} = (X_2 - X_1)/SD_1$$

Where:

$X_2$  is the domain score for each individual at any study assessment time post Baseline

$X_1$  is the Baseline domain score for that individual

$SD_1$  is the domain standard deviation of the population at Baseline

A composite z-score for the 7 CDR domains will be calculated based on the individual domain scores as:

(Continuity of Attention z-score + Quality of Episodic Secondary Memory z-score - Response Variability z-score + Quality of Working Memory z-score - Power of Attention z-score - Cognitive Reaction Time - Speed of Memory z-score)/7

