**Table 3: Objectives and Endpoints (Study RVT-101-2001)**

Objective	Endpoint
Efficacy Primary	

 
To assess the effects of Intepirdine versus placebo on the Unified Parkinson’s Disease Rating Scale – Part III (UPDRS-III) after 24 weeks of treatment
 
	Change from baseline in the UPDRS- III total score at Week 24
Efficacy Secondary	

 
To assess the effects of Intepirdine versus placebo on cognition, including amnesic aspects of cognition, as measured by the ADAS-Cog-11 after 24 weeks of treatment
 
	Change from Baseline in ADAS-Cog-11 at Week 24

 
To assess the effects of Intepirdine versus placebo on global function as measured by the CIBIC+ after 24 weeks of treatment
 
	Total score of the CIBIC+ at Week 24
Tertiary Endpoints	

 
To assess the effects of Intepirdine versus placebo on activities of daily living as measured by the ADCS-ADL scale after 24 weeks of treatment
 
	Change from Baseline in the ADCS-ADL at Week 24

 
To assess the effects of Intepirdine versus placebo on the Basic and Instrumental subscores of the ADCS-ADL scale after 24 weeks of treatment
 
	Change from Baseline in the Basic and Instrumental subscores of the ADCS-ADL at Week 24

 
To assess the effects of Intepirdine versus placebo on the Unified Parkinson’s Disease Rating Scale – Part III, 5-item subscale (UPDRS-5) after 24 weeks of treatment
 
	Change from baseline in the UPDRS-5 total score at Week 24

 
To assess the effects of Intepirdine versus placebo on cognition as measured by the composite z-score of the 7-domains of the CDR computerized assessment system after 24 weeks of treatment (CDR System domains include Power of Attention, Continuity of Attention, Quality of Working Memory, Quality of Episodic Memory, Speed of Memory, Cognitive
 
	Change from Baseline in the composite z-score combining the 7 domains of the CDR computerized assessment system at Week 24

Objective	Endpoint
Reaction Time and Reaction Time Variability)	

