#### 9.3.1. MMRM

Primary treatment comparisons between Intepirdine and placebo will be performed on the change from Baseline to Week 24 using an MMRM with restricted maximum likelihood estimation, an unstructured covariance matrix, and the Kenward-Roger approximation for denominator degrees of freedom. The model will include terms for treatment, visit, treatment by

visit interaction, pooled geographic region, baseline MMSE score, the baseline value, and the baseline value by visit interaction.

- The region by treatment interaction term will be evaluated at the 10% level of significance; if the interaction term is found to be significant, it will be included in the MMRM model. Note, this applies to ALL MMRM models.
  - For the by-region Subgroup analyses, where, because the subgroup analyses by Region only include 1 region, the interaction makes no sense. The same MMRM model is also used for subgroups for the primary efficacy endpoint, as appropriate.

As additional supportive information, treatment differences at *each post baseline visit* will also be derived using the MMRM model; however, primary inferences will be drawn from treatment differences derived from the MMRM models at Week 24.

The estimated treatment difference (“Intepirdine 35mg – Placebo” and “Intepirdine 70mg – Placebo”) at each visit will be displayed in the summary of statistical analysis together with the 95% confidence interval and the associated p-value.

No imputation of the missing values will be performed for the primary analyses, ie, the data used in the analysis will be the actual observed responses at each visit.

Least Squares Means for each visit will also be presented with the standard error and the number of subjects contributing to the Least Squares Means. Least Squares Means and estimated treatment differences for each visit and the associated 95% confidence interval will be displayed graphically.

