#### **9.4. Analysis of the Secondary, Tertiary, and Exploratory Efficacy Endpoints**

Continuous variables will be analyzed in a fashion similar to that of the primary endpoint, using the MMRM methodology on the observed cases dataset as well as a Wilcoxon rank (nonparametric) test. For those endpoints that are collected only once on-treatment, as there are no repeated measurements, an ANCOVA will be used; however, it is intended that the PROC MIXED SAS procedure will be used in all cases to perform the analysis, as it is capable of both the ANCOVA and MMRM analyses.

When required, the ANCOVA will have effects for treatment, baseline variable score, baseline MMSE score, and geographic region. The observed case analysis will be considered the primary assessment of this variable.

No methods for imputation of missing values are planned for the exploratory endpoints. Exploratory endpoints will only be assessed using the MMRM analysis method.

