#### 9.4.2. Tertiary Endpoints

Tertiary efficacy endpoints include the following. Note that analysis will be performed for each protocol-scheduled time point for each analysis variable and method, but the focus will be on the Week 24 time point.

- Change from Baseline on UPDRS-5 at Week 24
  - MMRM on observed data (also on UPDRS subgroups)
  - Wilcoxon Rank test on observed data
- Change from Baseline on ADAS-Cog 13 at Week 24
  - MMRM on observed data
  - Wilcoxon Rank test on observed data
- Change from Baseline in the Total score, and the Basic, Instrumental, Independence subscores of the ADCS-ADL scale at Week 24
  - MMRM on observed data (also on Concomitant Parkinsonian Meds subgroups)
  - Wilcoxon Rank test on observed data
- Change from Baseline in the Total Composite z-score and in the actual score (NOT the z-scores) of each individual domain of the CDR computerized assessment system at Week 24. Thus, in addition to the Total Composite, this includes the following 7 domains:

Power of Attention
Continuity of Attention
Cognitive Reaction Time
Response Variability
Quality of Working Memory
Quality of Episodic Secondary Memory
Speed of Memory

- MMRM on observed data
- Wilcoxon Rank test on observed data
- Change from Baseline in COWAT total score at Week 24

- MMRM on observed data
- Wilcoxon Rank test on observed data
- Change from Baseline in a composite z-score of the 7 CDR System domains plus the COWAT total score at Week 24
  - MMRM on observed data
  - Wilcoxon Rank test on observed data
- Change from Baseline in the sum of Parts A and B (Delusions and Hallucinations), and the sum of Parts of D and E (Depression and Anxiety) of the NPI at Week 24
  - MMRM on observed data
  - Wilcoxon Rank test on observed data
- Change from Baseline on the total severity score and distress score of the NEVHI score at Week 24 for subjects with visual hallucinations
  - MMRM on observed data
  - Wilcoxon Rank test on observed data
- Number (%) of patients with shifts from baseline in the NEVHI Total Severity Score and in the Distress Score (ie, 2 separate analyses) at Week 24, using a CMH row means score (CHM RMS) test. The categories for shifts are ordered as:
  - worsening from baseline
  - remaining unchanged from baseline
  - improving from baseline.

*Sample* SAS code for the CMH RMS is as follows (where MMSEbase is the baseline randomization stratum level for the patient, NOT the actual MMSE value):

```
Proc freq data=dat;  

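### The CDR composite z-score is already a change from the subject's own baseline, so the planned baseline adjustment has nothing to work on and precision is lost

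*SAP*

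**What the plan says.** **Definition.** SAP 5.13 (below Table 13) and Protocol 8.3.1.5 (below Table 4) set the domain z-score to (X2 - X1)/SD1. The three inputs are: "X2 is the domain score for each individual at any study assessment time post Baseline"; "X1 is the Baseline domain score for that individual"; and "SD1 is the domain standard deviation of the population at Baseline". The composite is the signed sum of the seven z-scores divided by 7. If one domain is missing, SAP 5.13 replaces its z-score with the average of the other six; if more than one is missing, the composite is missing.

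**Endpoint.** SAP Table 3 lists "Change from Baseline in the composite z-score combining the 7 domains of the CDR computerized assessment system at Week 24". SAP 9.4.2 repeats it: "Change from Baseline in the Total Composite z-score and in the actual score (NOT the z-scores) of each individual domain". So the composite is analysed as a z-score and the individual domains as raw scores.

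**Model.** SAP 9.4 states: "Continuous variables will be analyzed in a fashion similar to that of the primary endpoint, using the MMRM methodology". The primary model in SAP 9.3.1 contains treatment, visit, their interaction, and then "visit interaction, pooled geographic region, baseline MMSE score, the baseline value, and the baseline value by visit interaction". The sample code in SAP 9.3.1.1 carries matching baseline and baseline-by-visit terms. SAP 9.4.1 removes these terms for CIBIC+. No such exception is made for the CDR composite, and neither document defines a baseline composite or a substitute covariate.

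**The concern.** The baseline is subtracted inside the z-score, and the plan then asks for a change from baseline in the result and for adjustment on its baseline value. No usable baseline value exists. The adjustment that the SAP intends for continuous change endpoints is lost through a definition, not through a stated decision. The raw domain scores keep theirs, so the composite and its components are analysed under different effective models.

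What is at stake is precision. A change score subtracts the whole of any chance baseline difference, which over-corrects when the correlation is below 1, and the baseline covariate would have removed the remainder. There is also a programming risk, because the text leaves open whether the baseline value is zero or missing.

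**Working it through.** The plan states no SD, effect, power or correlation for the composite, so there is no figure of its own to reproduce. The check is algebra plus an illustration on assumed correlations.

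**1. Value at baseline.** Put X2 = X1: every domain z-score is (X1 - X1)/SD1 = 0, so the composite is 0 for each subject. Change from baseline in the composite then equals the composite itself. Strictly, X2 is defined only after baseline, so the alternative reading is that the baseline composite does not exist.

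**2. Effect on the model.** SAP Table 2 schedules the CDR at Weeks 4, 8, 12, 18 and 24. Three arms by five visits give a treatment-by-visit design of rank 15. Adding one zero baseline column and five zero baseline-by-visit columns leaves the rank at 15. In a simulated Week 24 data set the treatment estimate was -0.0477 with SE 0.0794, both with and without the zero baseline. If the baseline is coded as missing, both response and covariate are missing and PROC MIXED excludes every record.

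**3. Variance forgone, ignoring MMSE.** Let r be the correlation of the baseline and Week 24 composites, with unit variance at both times (assumptions).
- Unadjusted change: Var = 2(1 - r).
- Adjusted for baseline: Var = 1 - r² = (1 - r)(1 + r).
- Ratio = (1 + r)/2: 0.80 at r = 0.6 and 0.90 at r = 0.8.

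A simulation with 80 subjects per arm and an assumed between-domain correlation of 0.4 agrees:

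| r | (1 + r)/2 | simulated ratio |
|---|---|---|
| 0.5 | 0.75 | 0.76 |
| 0.6 | 0.80 | 0.80 |
| 0.7 | 0.85 | 0.85 |
| 0.8 | 0.90 | 0.90 |
| 0.9 | 0.95 | 0.95 |

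**4. Variance forgone, with baseline MMSE kept.** Let c be the correlation of MMSE with the baseline composite, and let MMSE predict Week 24 only through that composite (assumptions). The covariance of the change with MMSE is rc - c = -c(1 - r).
- Change given MMSE: Var = 2(1 - r) - c²(1 - r)².
- Change given MMSE and baseline composite: Var = 1 - r².
- Ratio = (1 + r)/(2 - c²(1 - r)).

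| r | c | ratio | variance cut |
|---|---|---|---|
| 0.6 | 0.5 | 1.6/1.900 = 0.84 | 16% |
| 0.6 | 0.7 | 1.6/1.804 = 0.89 | 11% |
| 0.8 | 0.5 | 1.8/1.950 = 0.92 | 8% |
| 0.8 | 0.7 | 1.8/1.902 = 0.95 | 5% |

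**5. Chance imbalance.** If the arms differ by d at baseline, the expected Week 24 carry-over is rd. The change score retains rd - d = -(1 - r)d, which is -0.4d at r = 0.6 and -0.2d at r = 0.8. It averages zero over randomisation.

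**A wording slip.** Both documents omit the label on one term of the composite ("Cognitive Reaction Time - Speed of Memory z-score)/7"). Read literally, a raw value in milliseconds would enter and the baseline would not be zero. The surrounding text describes seven z-scores, so this is treated as a slip that should be corrected at the same time.

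**The case against.** The best defence is that little depends on this. The endpoint is tertiary: it is outside the testing sequence in SAP 7.5 and was not a basis for the sample size in SAP 6. All seven domains are also analysed as raw scores with working baseline adjustment. Baseline MMSE stays in the composite's model, and the model wording is flexible: SAP 9.4 asks only for a similar analysis, and the code is labelled a sample. All of this stands and limits the consequence. The flexibility does not supply a baseline value, though, and a programmer would have to invent one.

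A reader might also infer more than the documents support:
- *That chance baseline imbalance goes uncorrected.* It does not. The change score subtracts all of it; only the -(1 - r)d over-correction remains.
- *That a zero baseline is certain.* The formula covers post-baseline assessments only, so zero is one programming outcome.
- *That the CDR plus COWAT composite has the same defect.* Neither document gives its formula or says how COWAT is standardised.
- *That the gain is 10 to 20%.* That holds only if MMSE explains nothing.
- *That composites could be rebuilt at each visit and differenced with no effect on the response.* This fails under the missing-domain rule. If the seventh domain is missing only after baseline, a subject's value shifts by (mean of the other six sign-aligned baseline z-scores minus the seventh)/7. With a 2 SD gap, that is 2/7 = 0.29.

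**Conclusion.** The point holds as a loss of precision and an undefined baseline on one tertiary endpoint. It is not a bias: the composite is a valid change score, the randomised comparison is unbiased, and no primary or secondary conclusion is touched. The algebra in steps 1 and 2 needs only the plan's own formula. The size rests on assumptions, because the documents give no correlations. With r of 0.6 to 0.8, equal variances, and MMSE correlated 0.5 to 0.7 with the baseline composite and acting only through it, adjustment would cut the variance by about 5 to 16%. The gain shrinks as r rises. It is worth taking because it costs nothing.

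**What to change.** In SAP 5.13 and 9.4.2:
1. Keep the composite as defined, including its missing-domain rule, as the response, and state that it is itself the change from baseline.
2. Define a separate baseline composite from (X1 - mean of all subjects at baseline)/SD1 for each domain, with the same signs and the same divisor of 7. State the population used for the mean and SD1, and the rule for a domain missing at baseline.
3. Enter that baseline composite and its by-visit interaction as the baseline terms in the MMRM.
4. State the formula for the CDR plus COWAT composite. Apply the same covariate approach there only if it is built from own-baseline z-scores.
5. Correct the label on the Cognitive Reaction Time term.

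Align Protocol 8.3.1.5, or rely on the rule in SAP 7.3 that the SAP prevails where the two differ. The cost is a few sentences of text and minor programming before unblinding. No new data are needed, and the treatment-effect scale does not change.
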